4.4.4 Additional Restrictions

Activity restrictions:

- Patients should abstain from strenuous exercise and avoid noisy environments (e.g., hair dryer, lawn equipment, open windows while driving, cinemas, listening to music, etc.) while the VitaloJAK cough monitor is attached over a 24-hour period. However, patients may participate in light recreational activities (e.g., watching television at a low volume, reading).
- Patients should not allow the VitaloJAK cough monitor, microphone, or chest sensor to get wet. Thus, they must avoid bathing or showering for the duration of the 24-hour recording.

The VitaloJAK chest sensor will be applied to the patient's chest with an adhesive (sticky pad). If the patient has a known allergic sensitivity or reaction to adhesives, and in the opinion of the investigator the sensitivity or reaction is severe enough to impact the ability of the patient to complete the study, the patient should not be enrolled in this study.

See the VitaloJAK site manual for further details.

- Patients should avoid vigorous exercise on the day of mannitol challenge test prior to administration.
- Patients should not consume caffeine within 12 hours prior to each mannitol challenge test.

Medication restrictions before provocation with mannitol:

- SABAs (short-acting β -agonists) within 8 hours prior to each mannitol challenge
- ICS within 12 hours prior to each mannitol challenge
- Ipratropium bromide within 12 hours prior to each mannitol challenge
- Non-steroidal anti-inflammatory medications within 12 hours prior to each mannitol challenge test.
- Twice daily LABAs or ICS/LABAs within 24 hours prior to each mannitol challenge
- *Xanthines (e.g., theophylline, oxtriphylline) within 24 hours prior to each mannitol challenge*
- Tiotropium bromide within 72 hours prior to each mannitol challenge
- Oral antihistamines within 72 hours prior to each mannitol challenge
- Leukotriene-Modifiers within 4 days prior to each mannitol challenge

4.5 STUDY ASSESSMENTS

The schedule of activities to be performed during the study is provided in [Appendix 1](#). All activities should be performed and documented for each patient.

Patients will be closely monitored for safety and tolerability throughout the study. Patients should be assessed for toxicity prior to each dose; dosing will occur only if the clinical assessment and local laboratory test values are acceptable.

At applicable sites, certain study assessments such as blood draws may be performed by an MN professional at the patient's home or another suitable location to improve access and convenience for patients participating in the study. The Sponsor will select a healthcare company that will be responsible for providing MN services for participating sites (the MN vendor). The MN vendor is responsible for ensuring that all MN professionals are licensed, qualified, and in good standing, as per applicable regulations, and that appropriate background checks have been performed. If the investigator at a participating site determines that MN services are appropriate for a patient and the patient gives written informed consent to participate in MN visits, the MN network will communicate with the patient and the patient's site. MN visits will be scheduled on specified visit days, to allow for relevant assessments to be performed by the MN professional. The schedule of activities (see [Appendix 1](#)) will specify the assessments that may be performed by an MN professional.

4.5.1 Informed Consent Forms and Screening Records

Written informed consent for participation in the study must be obtained before performing any study-related procedures (including screening evaluations). Informed Consent Forms for enrolled patients and for patients who are not subsequently enrolled will be maintained at the study site.

All screening evaluations must be completed and reviewed to confirm that patients meet all eligibility criteria before enrollment. The investigator will maintain a detailed record of all patients screened, to document eligibility or record reasons for screening failure, as applicable.

4.5.2 Medical History, Baseline Conditions, Concomitant Medication, and Demographic Data

Medical history, including clinically significant diseases, surgeries, cancer history (including prior cancer therapies and procedures), historical record of post-bronchodilator reversibility of FEV₁ or documented methacholine positive test, history of acute exacerbations (asthma or COPD), reproductive status, smoking history, and use of alcohol and drugs of abuse, will be recorded at baseline. In addition, all medications (e.g., prescription drugs, over-the-counter drugs, vaccines, herbal or homeopathic remedies, nutritional supplements) used by the patient within 14 days prior to initiation of study treatment will be recorded. At the time of each follow-up physical examination, an interval medical history should be obtained and any changes in medications and allergies should be recorded.

Demographic data, including age and sex, will be also recorded at baseline, along with self-reported race/ethnicity, sexual orientation, and gender identity for patients willing to provide this information (U.S. sites only).

4.5.3 Physical Examinations

A complete physical examination, performed at screening and other specified visits, should include an evaluation of the head, eyes, ears, nose, and throat, and the cardiovascular, dermatologic, musculoskeletal, respiratory, gastrointestinal, and neurologic systems. Any abnormality identified at baseline should be recorded on the General Medical History and Baseline Conditions eCRF.

Limited, symptom-directed physical examinations should be performed at specified postbaseline visits and as clinically indicated. Changes from baseline abnormalities should be recorded in patient notes. New or worsened clinically significant abnormalities should be recorded as adverse events on the Adverse Event eCRF.

Sensory neurologic examinations, including assessment of light touch, pain, vibration, temperature, and two-point discriminative sensations, will be performed at screening and other specified timepoints to identify potential changes in the peripheral sensory system. TRPA1 is expressed on peripheral terminals of nociceptive primary sensory neurons, where it is involved in the transduction of potentially harmful stimuli. In addition, TRPA1 is involved in amplification of nociceptive transmission in the central terminals of nociceptive primary sensory neurons.

New or worsened clinically significant abnormalities should be recorded as adverse events on the Adverse Event eCRF.

4.5.4 Vital Signs

Vital signs will include measurements of respiratory rate, pulse rate, and systolic and diastolic blood pressure (BP) while the patient is in a seated position, and temperature. Record abnormalities observed at baseline on the General Medical History and Baseline Conditions eCRF. At subsequent visits, record new or worsened clinically significant abnormalities on the Adverse Event eCRF.

4.5.5 Mannitol Challenge Test

The mannitol challenge test is a commercially approved bronchial challenge test kit containing pre-filled mannitol capsules and a handheld dry powder inhaler device. During a mannitol challenge test, patients will orally inhale increasing doses of mannitol. After each dose, airway parameters will be measured by spirometry. Inhalation of mannitol doses will continue until all doses (cumulative 635 mg) are inhaled, *there is a ≥15% decrease in FEV₁ relative to baseline, or there is a ≥10% decrease in FEV₁ between two successive doses. The mannitol challenge test is required at Study Visit 1 (screening) and optional at Study Visits 4 and 7 (see Section 4.5.14).* Details regarding conduct of mannitol challenge are provided in the mannitol challenge test guidance.

4.5.6 Cough Monitoring

Objective cough counting will be conducted as per the study's pulmonary function and cough monitoring guidance documents, in addition to standard manual methods of counting during the mannitol challenge tests (Koskela et al. 2004; Koskela et al. 2018). Cough numbers will be assessed by the VitaloJAK (Vitalograph Inc.) semi-automated cough-monitoring system. The VitaloJAK device will record ambulatory audio for 24 hours from two channels, a lapel microphone (air) and a chest-facing sensor (skin). A software algorithm will remove non-cough sounds from the 24-hour audio recordings, compressing the files to less than 10% (on average) of the original length enabling manual analysis to be completed more quickly. The recordings will be reviewed by trained Vitalograph analysts who will count individual explosive cough sounds, yielding hourly and 24-hour OCCs.

The VitaloJAK counting device will be provided to all study sites. The VitaloJAK device will be used to record spontaneous coughs during for 24 hours on the first day of screening, for 24 hours prior to the first dose of study drug of each treatment period, and for 24 hours following each optional mannitol challenge test during each treatment period (or for 24 hours beginning approximately 3 hours after study drug administration, if mannitol challenge test is not performed), as outlined in the schedule of assessments ([Appendix 1](#)). The pulmonary function and cough monitoring guidance documents will include information on equipment, procedures, patient instructions, and precautions regarding the use of the VitaloJAK. Cough monitoring will be performed per the study's cough monitoring guidance documents. Required training on equipment use and data transfer methods will be provided.

[REDACTED]

[REDACTED]

[REDACTED]

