For sampling procedures, storage conditions, and shipment instructions, see the laboratory manual.

Blood samples collected for WGS or WES are to be stored until they are no longer needed or until they are exhausted. However, the storage period will be in accordance with the IRB/EC-approved Informed Consent Form and applicable laws (e.g., health authority requirements).

Refer to Section 4.5.10 for details on use of samples after patient withdrawal and confidentiality standards for data.

Data generated from blood samples collected for WGS or WES will be analyzed in aggregate rather than on an individual patient basis. Thus, there will be no identification and reporting of incidental findings to investigators or patients.

If permitted by local law, a patient may request access to uninterpreted WGS or WES data derived from analysis of his or her blood sample. If a patient wishes to access these data, the investigator must inform the Sponsor, using the following email address: [contact]. The Sponsor will provide available data to the investigator in the form of a raw genomic sequencing data file, but will not provide any interpretation of the data. The investigator should not include the data file in the patient's medical record. Samples may be stored and analyzed in the future, and some samples may never be analyzed. Thus, data may not be available at the time of the request or may never be available.

The aggregate results of any conducted research will be available in accordance with the effective Sponsor policy on study data publication.

4.5.14 *Optional Mannitol Challenge Tests*

Consenting patients will undergo optional mannitol challenge tests during each treatment period at Study Visits 4 and 7. Each mannitol challenge test is to be performed at least 2.5 hours after study drug administration. Details on the mannitol challenge test are provided in Section 4.5.5 and in the mannitol challenge test guidance. See Section 4.5.6 for details on cough monitoring during the challenges. Medication restrictions prior to the mannitol challenge are provided in Section 4.4.4.

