6.4 EFFICACY ANALYSES

The purpose of this study is estimation and hypothesis generation regarding efficacy and activity of GDC-6599, as compared with placebo, in patients with CRC with asthma or UCC. The effects of GDC-6599 on cough will also be assessed in a subgroup of patients with CRC with COPD. Statistical summaries will be descriptive in nature (e.g., incidence rates, means, standard deviations, and percentiles). Any patients who received any amount of GDC-6599 or placebo will be included in the analyses. Patients will be grouped according to the treatment received in a given period. Final results will be summarized for GDC-6599 and for the placebo periods. No formal hypothesis testing will be performed.

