8.2 INFORMED CONSENT

The Sponsor's sample Informed Consent Form (and ancillary sample Informed Consent Forms such as an Assent Form or Mobile Nursing Informed Consent Form, if applicable) will be provided to each site. If applicable, it will be provided in a certified translation of the local language. The Sponsor or its designee must review and approve any proposed deviations from the Sponsor's sample Informed Consent Forms or any alternate consent forms proposed by the site (collectively, the "Consent Forms") before IRB/EC submission. The final IRB/EC–approved Consent Forms must be provided to the Sponsor for health authority submission purposes according to local requirements.

If applicable, the Informed Consent Form will contain separate sections for any optional procedures. The investigator or authorized designee will explain to each patient the objectives, methods, and potential risks associated with each optional procedure. Patients will be told that they are free to refuse to participate and may withdraw their consent at any time for any reason. A separate, specific signature will be required to document a patient's agreement to participate in optional procedures. Patients who decline to participate will not provide a separate signature.

The Consent Forms must be signed and dated by the patient or the patient's legally authorized representative before his or her participation in the study. The case history or clinical records for each patient shall document the informed consent process and that written informed consent was obtained prior to participation in the study.

The Consent Forms should be revised whenever there are changes to study procedures or when new information becomes available that may affect the willingness of the patient to participate. The final revised IRB/EC–approved Consent Forms must be provided to the Sponsor for health authority submission purposes.

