- t Details on the mannitol challenge test are provided in Section 4.5.5 and in the mannitol challenge test guidance. Medication restrictions prior to the mannitol challenge are provided in Section 4.4.4. If the optional mannitol challenge test is performed at Visit 4 and/or 7, it is to be performed at least 2.5 hours after study drug administration.

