Appendix 1: Schedule of Activities for Part A and Part B

- u Post-bronchodilator spirometry replaces the recovery spirometry assessment [*if required*] following mannitol challenge at screening. Post-bronchodilator spirometry should be performed per the pulmonary function and cough monitoring guidance documents at least 1 hour following the mannitol challenge test or on a separate study visit within the screening period before or after the mannitol challenge test.
- v Details on cough monitoring are provided in Section 4.5.6 and in the pulmonary function and cough monitoring guidance documents.
- w Cough monitoring with the VitaloJAK cough recorder will begin on the first day of screening and will continue for 24 hours if the screening visits occur over multiple visits. If screening visit occurs during a single visit, use of the VitaloJAK cough recorder should start at least 30 minutes after the mannitol challenge test.
- x Cough monitoring with the VitaloJAK cough recorder will begin a minimum of 24 hours prior to study drug administration and will conclude on the day of study drug administration.
- y Cough monitoring with the VitaloJAK cough recorder will begin at the *end of the mannitol challenge test* (i.e., immediately after spirometry following the last dose of mannitol or after the final spirometry following the recovery period [*if required*]) and will continue for 24 hours after mannitol challenge recovery period. If the mannitol challenge test is not performed, cough monitoring with the VitaloJAK cough recorder will begin approximately 3 hours after study drug administration.

z [REDACTED]

aa Study drug (GDC-6599 or placebo) will be administered [REDACTED] on Days 1–14 and on Days 30–43. [REDACTED]

bb [REDACTED]

[figure not shown]
cc [REDACTED]

[figure not shown]
dd After informed consent has been obtained but prior to initiation of study drug, only serious adverse events caused by a protocol-mandated intervention should be reported. After initiation of study drug, all adverse events will be reported until 28 days after the final dose of study drug.

[figure not shown]
Reference:

[figure not shown]

[figure not shown]

[figure not shown]

Appendix 6

Visual Analog Scale

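### The primary 24-hour cough recording at Visits 4 and 7 can follow an optional mannitol challenge with no minimum gap, and Section 6.4 does not mention challenge status

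*Combined protocol and SAP*

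**What the plan says.** The primary endpoint (Section 2, Table 1) is the change in coughs per hour, counted over 24 hours, from baseline to Day 14. Visits 4 (Day 14) and 7 (Day 43) supply the end-of-period recordings. Section 4.5.6 describes what is recorded as spontaneous cough.

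The start rules for the recorder are these:

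- **Visits 4 and 7, challenge done.** Section 4.5.6 records "for 24 hours following each optional mannitol challenge test during each treatment period". Footnote y of Appendix 1 defines the start as "immediately after spirometry following the last dose of mannitol or after the final spirometry following the recovery period", the second alternative applying if recovery is required. No minimum interval is given.
- **Visits 4 and 7, no challenge.** Recording starts about 3 hours after dosing (Section 4.5.6, footnote y).
- **Single-visit screening.** Footnote w says that "use of the VitaloJAK cough recorder should start at least 30 minutes after the mannitol challenge test"; footnote a says the same.
- **Pre-dose recordings.** Footnote x: "Cough monitoring with the VitaloJAK cough recorder will begin a minimum of 24 hours prior to study drug administration". Appendix 1 schedules no challenge before them.

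On who is challenged, Section 4.5.14 states: "Consenting patients will undergo optional mannitol challenge tests during each treatment period at Study Visits 4 and 7". Footnote t, a timing instruction, begins: "If the optional mannitol challenge test is performed at Visit 4 and/or 7". For optional procedures, Section 8.2 says patients are "free to refuse to participate and may withdraw their consent at any time for any reason".

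On analysis, Section 6.4 states: "Patients will be grouped according to the treatment received in a given period". It does not mention challenge status. Summaries are descriptive and no hypothesis is tested.

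**The concern.** Every enrolled patient has been selected for coughing in response to mannitol (Section 4.1.1.1 requires at least 12 coughs per 100 mg). In those who take the optional test and need no recovery period, the primary recording opens directly after that stimulus. If some provoked cough persists, it is counted as spontaneous cough. Patients with a positive response or significant respiratory symptoms receive a SABA (Section 5.1.2.1), which could also affect the count, and not necessarily upwards.

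The protocol separates challenge and recorder by 30 minutes at single-visit screening, but not at the two visits that supply the primary endpoint. Because Section 6.4 does not mention challenge status, nothing in the planned summaries would show whether the two kinds of Day 14 recording differ. At stake is avoidable noise, and in some circumstances a small bias, in an endpoint whose day-to-day variability Section 3.3.6 already calls significant.

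**Working it through.** The plan gives no figure to reproduce: Section 6.1 states 20 to 30 patients per cohort without an effect size or standard deviation. The check is therefore algebra plus a conversion for scale.

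**1. When the after-effect matters.** For one patient, let e_G and e_P be the extra coughs carried into the recording after a challenge on GDC-6599 and on placebo. Let c_G and c_P be 1 if challenged in that period and 0 if not. Then

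observed difference = true difference + (c_G × e_G − c_P × e_P) / 24.

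- Challenged in both periods, e_G = e_P: the extra term is 0.
- Challenged in one period only: the extra term is +e/24 or −e/24, depending on which treatment that period held.
- Challenged in both periods, GDC-6599 cutting the after-effect by a fraction s: the extra term is −s × e_P / 24. Section 3.3.5 says the study will test whether mannitol-induced cough depends on TRPA1, so s is open.

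Even where the treatment difference is clean, a challenge shifts the within-period change from baseline by e/24, because the pre-dose recording has no challenge before it.

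**2. Conversion.** 10 lingering coughs: 10/24 = 0.42 coughs/h in that recording. 20 coughs: 20/24 = 0.83 coughs/h. For context, at the entry threshold and the full 635 mg (Section 4.5.5) a challenge provokes 12/100 × 635 = 76.2 coughs, so 20 would be 20/76.2 = 26% of that number.

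**3. Part A mean (60 patients), under assumptions.** None of the inputs in this step except the 60 patients and the 76.2 coughs comes from the documents, and zero is possible throughout.

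- *One-period challenges, chance imbalance only.* Assume m = 6 to 15 such patients. The 95% range of net imbalance is 1.96 × √m = 4.8 to 7.6 patients. The shift is 4.8 × 0.417/60 = 0.03 to 7.6 × 0.417/60 = 0.05 coughs/h at 10 lingering coughs, and 0.07 to 0.11 at 20.
- *Both periods challenged, half of patients opting in, s = 20% to 50%.* 0.5 × 0.2 × 0.417 = 0.04 to 0.5 × 0.5 × 0.417 = 0.10 coughs/h at 10 lingering coughs; 0.08 to 0.21 at 20.
- *An extreme set.* All patients challenged twice, lingering cough equal to half of the 76.2 (38.1) and s = 50%: 38.1 × 0.5/24 = 0.79 coughs/h.

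The span from 0 to 0.79 is a span of assumptions, not an estimate.

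**4. Effect of a 30-minute gap on timing.** The challenge starts at least 2.5 hours after dosing (Section 4.5.14). With the gap, the recorder would start at 2.5 + 0.5 = 3.0 hours plus the duration of the challenge, which is later than the roughly 3 hours used without a challenge.

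**5. Data kept in a sensitivity estimate that drops 2 hours.** 22/24 = 92% of each recording.

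**The case against.** The strongest reply is that no passage documents cough persisting after the final spirometry. Section 3.3.5 speaks of coughing on inhalation, challenge coughs are counted separately by hand (Section 4.5.6), and the recorder starts only once the challenge is over. Section 4.5.14 plans the test in both periods, so an equal after-effect would cancel. The study is descriptive and hypothesis-generating. Separate cough monitoring and mannitol guidance documents, and the redacted end of Section 4.5.6, may already set a gap. Unchallenged patients also have spirometry at least 2.5 hours after dosing (footnote s), so the two pathways are closer in time than they first look.

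Most of this stands, and it limits the size of the point. It does not remove the rule itself: footnote y gives a start with no interval, and any gap set in the guidance would need reconciling with it.

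A reader might infer more in three places, and the documents do not support it:

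- *That footnotes w and y contradict each other.* They govern different recordings. The screening rule is an analogy, and the documents do not show that 30 minutes is long enough.
- *That Section 6.4 prescribes pooling.* It does not mention challenge status and does not bar a breakdown.
- *That one-period challenges are planned.* The and/or in footnote t sits in a timing instruction. One-period challenges are more likely to come from a missed test or withdrawn consent.

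**Conclusion.** The point holds as a minor, cheap improvement. As written, the primary recording at Visits 4 and 7 can follow a cough-provoking test with no minimum gap, while single-visit screening has one, and the analysis section does not distinguish the two kinds of recording.

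Size and direction cannot be derived from the documents. They give no duration of post-challenge cough, no uptake of the optional test and no baseline cough rate. The conversion of 0.42 coughs/h per 10 lingering coughs is arithmetic; everything beyond it rests on assumed inputs. A one-period challenge mainly adds noise. It biases the mean only if such challenges are unbalanced by treatment. In patients challenged twice, bias in the treatment difference needs an after-effect that GDC-6599 changes.

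It would be tempting to conclude that the primary endpoint is biased or that the study's conclusions are at risk. The documents do not support that: persistence of provoked cough is not shown, an equal after-effect cancels in the absolute treatment difference, and no formal test depends on the result.

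**What to change.** 1. **Timing.** Amend Section 4.5.6 and footnote y so that the Visit 4 and 7 recorder starts at least 30 minutes after the end of the challenge, as in footnote w. Alternatively, reconcile the two footnotes with the cough monitoring guidance and state the reason for any difference.
2. **Analysis.** In Section 6.4, tabulate challenge status by period and treatment. Add one sensitivity estimate of the primary endpoint on pooled Part A data, dropping the first 2 hours of each post-challenge recording and the same clock hours of the recordings it is compared with. Section 4.5.6 already yields hourly counts. Flag patients challenged in one period only and patients given a SABA after the challenge. Neither the gap nor the 2-hour drop can be assumed to remove a SABA effect: Section 4.5.7 itself requires 8 hours between a SABA and spirometry.
3. **Wording.** Align the and/or in footnote t with Section 4.5.14. Nothing further is needed there.

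The cost is text changes and no new assessments. Challenged patients may have a visit up to about 30 minutes longer, and their recorder would start somewhat later after dosing than the roughly 3 hours used for unchallenged patients. The sensitivity estimate uses 92% of each recording.
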